Once diagnosed, in order to be treated, patients must see a physician and undergo the various tests and laboratory analyses mentioned above. The patient who engages in this process is considered to be "linked-to-care". However, many patients do not consult or quickly disengage from follow-up. A US study reported that 47% of patients who know their status do not link to the health care system.³ The often long delays between diagnosis and clinical management contribute to the current loss to follow-up. For example, one Canadian study reported delays of 66.3 months from initial diagnosis to referral to a specialty, an additional 1.5 months to seeing the specialist, and 6.8 months from initial visit to initiation of treatment.¹⁵ Another Canadian study reported loss-to-follow-up rates of 19% during evaluation, while a Scottish study noted that 16% of patients never made it to the first visit and 24% were lost after only one visit.^{16,17} It is therefore important to assess whether expediting management would allow more patients to initiate treatment by limiting disengagement from care.

The goal of the first project is to evaluate the feasibility of routine HIV and HCV screening using an opt-out approach in the CHUM emergency department and to determine the rate of new HIV and HCV diagnoses. A sub-analysis will focus more specifically on HCV in the Quebec equivalent of the baby boomers (1945-1975), since this is the group that was targeted in the United States.¹⁸ We also want to evaluate the effectiveness of linkage-to-care for people diagnosed with HIV or HCV and the speed with which these people are taken into care and put on treatment.

Hypothesis:

We believe that it is realistic to observe a proportion of new diagnoses greater than 1/1000 for HIV and 1/100 for HCV in the CHUM emergency department.

Objectives:

Primary objectives

1. To determine the prevalence of new HIV and HCV diagnoses among the patients visiting the CHUM emergency department
2. To determine the overall prevalence of HIV and HCV (new cases and known cases) among the patients visiting the CHUM emergency department

Secondary objectives

1. To determine the prevalence of new and known HCV cases among the "baby boomers" (41-73 years)
2. To determine the proportion of adherence of ED staff to the offer of HIV and HCV testing
3. To determine the proportion of patients "opting out" of routine HIV and HCV testing in the ED

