The research nurse will check the hospital's computer system to see if the patient has been seen in a specialty clinic within one month of the positive test announcement. If not, the research nurse will follow up with the patient by phone to see if they have been seen outside the hospital for this new diagnosis. If after three attempts to call, the patient is not reached, they will be considered not linked to the health care system. For HIV patients, she will check for confirmatory

serology, viral load, and CD4 count and whether treatment has been initiated. For HCV, she will verify that RNA testing and, if applicable, genotyping have been performed. For chronic HCV patients, she will assess at 3 months whether liver fibrosis has been assessed and whether treatment has been prescribed.

Eligibility criteria for the cross-sectional HIV/HCV screening component of the study:

Inclusion criteria :

Individuals between the ages of 18 and 73 years consulting the CHUM emergency department regardless of the time of consultation.

Exclusion criteria :

Persons unable to refuse the test, notably because of their medical condition leading them to consult the emergency room.

If the person's condition improves during the emergency room visit, they may be offered screening at that time.

Eligibility criteria for the linkage-to-care of HIV/HCV-infected patients component of the study:

Inclusion criteria:

- Patient who has agreed to HIV or HCV test(s) in the UHC emergency department.
- Aged 18 years to 73 years
- Tested positive for HIV and/or HCV
- Able to consent and sign the information and consent form

Outcomes:

Primary outcomes

1. Prevalence of unknown HIV or HCV infections in the CHUM emergency department during the study period: positive tests / tests performed in unknown patients with HIV or HCV
2. Overall prevalence of HCV and HIV during the study period: (positive tests + known positive cases) / (tests performed + known positive cases)

Secondary outcomes

1. For HCV, among baby boomers (1945-1975 or 43-73 years)
 - a. Prevalence of new cases (positive tests/tests performed)
 - b. Overall prevalence (positive tests + known positive cases) / (tests performed + known positive cases)
2. Staff adherence: (tests performed, refused or known positive) / (eligible patients)
3. Proportion of patient opt-outs: tests refused / (tests performed + tests refused)

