The sample size was based on the threshold prevalence of newly diagnosed HIV infection that warrants the implementation of a routine HIV testing program (1/1000 according to the CDC). Assuming a prevalence of undiagnosed cases of 1/1000, a study of 4,000 subjects would yield a 95% confidence interval of 0.3/1000 to 2.7/1000. For HCV, assuming a prevalence of undiagnosed cases of 1/100, we will obtain a 95% confidence interval between 0.7 and 1.3%. In 2014-2015, 110 420 consultations took place in the CHUM emergency department.²⁰ Patients were between 18 and 74 years of age in 85% of cases,²⁰ which represented 93 857 consultations per year (7821/month). Few studies have reported missed opportunities for screening in emergency department opt-out situations. One study reported 49.9% missed opportunities due to either staff oversight or patient refusal.¹¹ In other studies, patient refusal rates were in the range of 30-35%.^{8,9} Assuming a proportion of patient refusal and staff oversight of 50%, the recruitment period should be a maximum of 2 months.

Analyses

Descriptive statistics with 95% confidence intervals will be used to calculate, separately for HIV and HCV, the prevalences of new and known cases and the proportions of "opt-out" and staff adherence to testing. The prevalences of new and known HCV cases among baby boomers will be calculated in the same way. Medians and their confidence intervals will be calculated for the time required to inform the patient of the screening and for the time required to announce the result. Program costs will be presented in absolute terms and as a cost per newly diagnosed case. Liaison with a specialized team, completion of the initial workup and initiation of treatment at one month (HIV) or three months (HCV) will also be presented as proportions with their confidence intervals.

Ethical and Regulatory Considerations

Research Ethics Board

The protocol, forms and regulatory documents will be submitted to and approved by the CHUM Research Ethics Committee and Scientific Committee.

Information and consent form

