if only people who use drugs were to be screened, this would not likely be the case for the prevalence of new cases, as the screening service for people who use drugs in Montreal is already well established. Although similar projects have been carried out in the United States, it is important not to make inferences from the epidemiological data established there. The different context of care in Quebec, including free health care and possibly easier access to screening, may have a major impact on the prevalence of new cases that we will establish. Expanded screening may not be as cost-effective in Quebec as in the United States.

In terms of limitations, it is possible that patients who come to us for reasons that do not warrant blood sampling will refuse the test more often than those who need it. The former group of patients may be healthier, so there may be a bias towards an increase in the observed prevalence. Since the same situation is likely to occur in real practice, our results will still be valid. The night-time clientele may be different from the daytime clientele. It is important that nurses on different shifts adhere to the protocol in the same way to avoid bias. Training will therefore be given to all shifts. Like all serological tests, those used have a window period and may miss acute cases, thus reducing the observed prevalence of new cases. However, the tests used are those with the shortest window period available on the market. Finally, the clientele consulting the emergency room varies greatly depending on the geographic location of a hospital. The results obtained at the CHUM may not be generalizable to other hospitals and a second multicentre project will be necessary if the initial targets are met. This second phase will better establish the prevalence of new cases and the cost-effectiveness of screening in EDs serving populations with fewer traditional risk factors for HIV or HCV than CHUM.

References

2. 90-90-90. An ambitious treatment target to help end the AIDS epidemic. (Accessed 5 septembre 2016, at http://www.unaids.org/sites/default/files/media_asset/90-90-90_en_0.pdf.)

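### The primary estimate is the yield among patients tested, but primary objective 1 is prevalence among ED visitors, and the plan's validity argument does not bridge the two

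*Combined protocol and SAP*

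**What the plan says.** Primary objective 1 (Objectives) is "To determine the prevalence of new HIV and HCV diagnoses among the patients visiting the CHUM emergency department". The screening component admits "Individuals between the ages of 18 and 73 years consulting the CHUM emergency department regardless of the time of consultation", less those unable to refuse the test. Primary outcome 1 (Outcomes) is "positive tests / tests performed in unknown patients with HIV or HCV", so patients who refuse or are missed enter neither the numerator nor the denominator.

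The Sample size section puts refusal and staff oversight together at 50% when it sets the recruitment period. It cites one study with 49.9% missed opportunities and others in which refusal alone was 30-35%.

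The section on strengths and limitations raises the possibility that patients whose complaint needs no blood sample decline more often, and that they are in better health. From this it infers that "there may be a bias towards an increase in the observed prevalence". The next sentence is "Since the same situation is likely to occur in real practice, our results will still be valid".

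The Analyses section plans descriptive proportions with 95% confidence intervals. Opt-out and staff adherence are secondary outcomes. No comparison of tested with untested patients, no weighting or standardisation, and no bounds are planned. Under Data collection, the triage sheets supply age, zip code, refusals and patients not approached. Shift, and whether blood was drawn for clinical care, are not listed.

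**The concern.** The appeal to real practice answers a different question from the one in the objective. If refusal in routine use resembles refusal in the study, then positives per test performed is a fair forecast of what an opt-out programme would find per test. It says nothing about infection among eligible patients who were not tested. The plan itself names a way in which those patients could differ.

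This matters because the Hypothesis section sets targets of more than 1/1000 for HIV and 1/100 for HCV, and the limitations section makes a second, multicentre project depend on meeting the initial targets. A tested-only figure at or just above a target, reported as visitor prevalence, could correspond to a value below the target among eligible visitors. The confidence interval would not show this, since it reflects sampling error only. The opt-out and adherence proportions show how many patients were untested, not whether they differ.

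**Working it through.** **1. The plan's own precision figures.** With 4,000 tested, the expected cases are 4,000 x 1/1000 = 4 (HIV) and 4,000 x 1/100 = 40 (HCV).
- HIV, 4/4,000: Agresti-Coull gives 0.29 to 2.67 per 1000, and Wilson with continuity correction 0.32 to 2.75. The stated 0.3 to 2.7 is reproduced.
- HCV, 40/4,000: the Wald interval is 1.00% ± 1.96 x √(0.01 x 0.99 / 4,000) = 1.00% ± 0.31 points, or 0.69% to 1.31%. The stated 0.7 to 1.3% is reproduced.

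**2. The untested share in the plan.** At 50% untested, 4,000 tests need 4,000 / 0.5 = 8,000 eligible visits. At the stated 7,821 per month that is 1.02 months, inside the stated maximum of 2. The 50% is therefore a working assumption of the design.

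**3. Link between yield and prevalence.** Let *u* be the untested share of eligible patients not known to be infected, and *r* the prevalence in the untested divided by that in the tested. Then

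prevalence among eligible = yield x [(1 − u) + u x r], and observed/true = 1 / [(1 − u) + u x r].

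The plan gives *u* = 0.5. It gives no value for *r*, so every *r* below is an assumption.

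| r (assumed) | eligible prevalence per observed 1.0 | observed/true |
|---|---|---|
| 0.5 | 0.75 | 1.33 |
| 0.75 | 0.875 | 1.14 |
| 1 | 1.00 | 1.00 |
| 1.5 | 1.25 | 0.80 |
| 2 | 1.50 | 0.67 |

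The unit is per 1000 for HIV and per 100 for HCV.

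**4. Refusal alone.** The stated mechanism concerns refusal, not oversight. If oversight is unrelated to infection (assumption), those offered the test represent the eligible group, and *u* becomes the refusal share among those offered. At *r* = 0.5, 30% refusal gives 1 / 0.85 = 1.18 and 35% gives 1 / 0.825 = 1.21.

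**5. Against sampling error.** Suppose the true values equal the targets and *r* = 0.5 with half untested.
- HCV would be observed at 1.33%, a shift of 0.33 points against a planned half-width of about 0.3. Under step 4 the shift is 0.18 to 0.21 points.
- HIV would yield 4,000 x 1.33/1000 = 5.3 cases instead of 4, which is small beside the planned interval.

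**The case against.** The strongest defence is that the plan evaluates a programme. The section on the information and consent form says so, the outcome states its denominator openly, and the goal of the project includes feasibility and the rate of new diagnoses. On that reading *valid* means valid for programme yield. This stands: the fault is a mismatch between objective and estimator, not a wrong calculation.

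Some safeguards also exist. Patients who need no blood drawn are still offered the test, the triage form prompts staff, and all shifts are trained. These may reduce selection, but they do not measure it.

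Four stronger readings are tempting, and the documents do not support them:
- *The plan admits that its estimate is biased.* The text is conditional throughout and gives no size. It also names a downward influence, the window period of the tests, so the net direction is unknown.
- *The target is every ED visitor.* Eligibility is limited to ages 18 to 73 and to those able to refuse.
- *Comparison with 1/1000 is plainly invalid.* The rationale words that threshold as undiagnosed infection in the setting, but the Sample size section words it as newly diagnosed infection, which can be read as yield.
- *The bias would drive a rollout decision.* The next step named is a second study, meant to establish prevalence better.

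Large inflation from selective refusal is also hard to reach. Assume that half of visits need blood, that oversight is unrelated to draw status, and that no patient needing blood refuses. With overall refusal of 30-35%, patients needing blood are at most 0.5/0.70 = 71% to 0.5/0.65 = 77% of those tested. If their prevalence is three times that of the others and the overall mean is 1, the strata are 1.5 and 0.5. The observed value is then 0.5 + 0.71 to 0.5 + 0.77, or 21-27% too high at most.

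**Conclusion.** The concern holds in a limited form. Positive tests over tests performed estimates the yield among patients tested. The argument from real practice does not make it the prevalence among eligible visitors, and nothing planned examines the gap.

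The documents fix neither the size nor the sign of the bias. The factor of 1.33 to 1.00 rests on 50% untested, as planned, and an assumed untested/tested ratio of 0.5 to 1. For HCV, the upper end is comparable to the planned half-width. For HIV, sampling error dominates. None of this makes the study invalid. It limits what the primary result may be called and how it may be set against the targets.

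Primary objective 2 names the same visitors, and its formula also drops refusers while counting known positives in full. Its denominator deserves a separate look and is not sized here.

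**What to change.** 1. Replace the validity sentence. Say that similar refusal in practice supports the yield of an opt-out programme, and report positive tests over tests performed as *yield among patients tested*. Either reword primary objective 1 to match, or claim visitor prevalence only together with the analyses in items 2 and 3.
2. Tabulate tested, refused and not-approached patients by age band and zip code from the triage sheets, and check the total against the SIURGE count of eligible patients. Add shift and clinical blood-draw status only if existing records hold them, or through one added form item completed at blood collection.
3. For HCV (about 40 cases expected), add one sensitivity analysis that standardises prevalence to the eligible population over a few broad strata: age band, and draw status if recorded. Add bounds from the formula above, using the observed untested share and a range of *r* stated in advance that extends above 1. For HIV (about 4 cases), give the bounds only.

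The cost is a small amount of extra data handling, one form item at most, and a somewhat wider standardised HCV interval. Standardisation corrects only for the strata recorded, and age alone does not capture the blood-draw mechanism, which is why the bounds are needed as well. The primary calculation and the sample size are unchanged.
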